**12.2.3 Adverse Events of Special Interest (AESI)**

The following SOC terms will be grouped into a Special Interest AE Group.

| Special Interest AE Group | SOCs  | PTs                        |
|----------------------------------|--|-----------------------------------|
| Nasal toxicities                 | Respiratory, thoracic and mediastinal disorders          | Nasal septum perforation          |
|                                  | Respiratory, thoracic and mediastinal disorders          | Nasal mucosal ulcer               |
|                                  | Respiratory, thoracic and mediastinal disorders(Primary) | Epistaxis                         |
| Ophthalmic toxicities            | Eye disorders  | -Open angle glaucoma
-Glaucoma |
|                                  | Investigations   | Intraocular pressure increased    |
|                                  | Eye disorders  | Cataract                          |
| Somnolence                       | Nervous system disorders(Primary)                        | Somnolence                        |
| Others                           | Nervous system disorders (Primary)                       | Dysgeusia                         |
|                                  | Nervous system disorders                                 | Headaches                         |

The following tables will be produced for AESI:

- Summary of Treatment Emergent Adverse Events of Special Interest (Safety Analysis Set)
- Summary of Treatment Related Emergent Adverse Events of Special Interest (Safety Analysis Set)
- Summary of Treatment Emergent Adverse Events of Special Interest by Severity (Safety Analysis Set)
- Summary of Treatment Emergent Adverse Events of Special Interest by Relationship to Study Treatment (Safety Analysis Set)

**12.2.4 Laboratory Data**

Clinical laboratory test data (hematology, biochemistry, and urinalysis), will be summarized for each visit at which laboratory assessments are done (Screening Visit [Visit 1], Week 30 [Visit 8], and Week 52 [Visit 12]).

## STATISTICAL ANALYSIS PLAN

|  |                                    |                                  |
|--|------------------------------------|----------------------------------|
| Protocol Number:
GPL/CT/2014/018/III
(Study No. GSP 301-303) | SAP Version Number:
Version 1.0 | SAP Version Date:
04-Apr-2017 |
|--|------------------------------------|----------------------------------|

Descriptive statistics (number of subjects, mean, standard deviation, median, minimum and maximum) will be presented for laboratory data as well as change from baseline by treatment and visit.

Baseline is defined as the last available lab values at Screening Visit [Visit 1].

In addition, values outside the normal range and values deemed as clinically significant by the Investigator will be listed. The number of subjects with values of potentially clinical significance determined by the investigator will be tabulated by treatment group and visit.

Shift tables will present changes from baseline in laboratory data (categorized as normal; abnormal, not clinically significant; and abnormal, clinically significant) to end of treatment.

All laboratory data will be listed by treatment and subject.

### 12.2.5 Pregnancy Test

All females of child bearing potential will have a urine pregnancy test at each visit.

Pregnancy test results will be listed by treatment and subject.

### 12.2.6 Vital Signs

Descriptive statistics (number of subjects, mean, standard deviation, median, minimum and maximum) will be used to summarize vital sign results and changes from baseline by treatment group and time point (Week 1 [Visit 2], Week 30 [Visit 8] and Week 52 [Visit 12]).

Baseline is defined as the last available vital signs at Randomization Visit [Visit 2].

Values outside the respective normal range and values deemed as clinically significant by the Investigator will be listed.

The number of subjects with values of potential clinical significance determined by the investigator will be tabulated by treatment group and visit.

Shift tables will present changes from baseline in vital signs (categorized as normal; abnormal, not clinically significant; and abnormal, clinically significant) to end of treatment.

All vital sign data will be listed by treatment and subject.

|  |                                    |                                  |
|--|------------------------------------|----------------------------------|
| Protocol Number:
GPL/CT/2014/018/III
(Study No. GSP 301-303) | SAP Version Number:
Version 1.0 | SAP Version Date:
04-Apr-2017 |
|--|------------------------------------|----------------------------------|

### **12.2.7 ECGs**

Descriptive statistics (number of subjects, mean, standard deviation, median, minimum and maximum) for ECG parameters and changes from baseline will be presented by treatment group.

Baseline is defined as the last available ECG values at Screening Visit [Visit 1].

Shift tables will present changes from baseline in ECG interpretation (categorized as normal; abnormal, not clinically significant; and abnormal, clinically significant) to end of treatment.

The number of subjects with values of potential clinical significance determined by the investigator will be tabulated by treatment group and visit.

All ECG data will be listed by treatment and subject.

### **12.2.8 Physical Examinations**

Descriptive statistics (frequency and percentage) will be used to summarize physical examination results by treatment group and time point (Screening Visit, Week 30 and Week 52).

In addition, the number of subjects with values of potential clinical significance determined by the investigator will be tabulated.

All physical examination data will be listed by treatment and subject.

### **12.2.9 ENT examination**

Descriptive statistics (frequency and percentage) will be used to summarize ENT examination results by treatment group and time point (Screening Visit, Week 30 and Week 52).

In addition, the number of subjects with values of potential clinical significance determined by the investigator will be tabulated.

All ENT examination data will be listed by treatment and subject.

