13.7.7 Focused Ears, Nose, and Throat and Eye Examinations

Descriptive statistics will be used to summarize ENT and eye examination results by treatment group and time point (Week 30 and Week 52). The number of subjects with findings of potential clinical significance will be tabulated. All ENT and eye examination data will be displayed in listings.

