### 4.0 Study Endpoints

#### 4.1 Primary Endpoints

- Proportion of subjects with treatment-emergent adverse events (TEAEs).
- Proportion of subjects with treatment-related TEAEs.
- Incidence, type, and severity of the TEAEs after 30 weeks of study treatment.
- Incidence, type, and severity of the TEAEs after 52 weeks of study treatment.
- Clinical laboratory assessments (hematology, serum biochemistry, and urinalysis) at baseline, Week 30, and Week 52.
- Vital signs, physical examinations (PE), and focused ears, nose, and throat (ENT) and eye examinations at baseline, Week 30, and Week 52.

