**Table 2: Overview of Planned Safety Analyses**

| Display Type                    | Data Displays Generated |        |         |
|---------------------------------|-------------------------|--------|---------|
|                                 | Table                   | Figure | Listing |
| Adverse Events           |                         |        |         |
| Overview                        | Y[2]                    |        |         |
| Treatment Emergent AEs          | Y[1][2]                 |        | Y       |
| Treatment Emergent AEs Severity | Y[2]                    |        | Y       |
| Drug-Related AEs                | Y[2]                    |        | Y       |
| Placebo Run-In Period AEs       | Y[2]                    |        | Y       |
| AEs Leading to Withdrawal       |                         |        | Y       |
| SAEs                            | Y[2]                    |        | Y       |
| Treatment Emergent SAEs         | Y[2]                    |        | Y       |
| Laboratory               |                         |        |         |
| Biochemistry                    | Y[3] [2]                |        | Y       |
| Haematology                     | Y[3] [2]                |        | Y       |
| Urinalysis                      | Y[3] [2]                |        | Y       |
| Pregnancy Test Results          |                         |        | Y       |
| Other                    |                         |        |         |
| Vital Signs                     | Y[4] [2]                |        | Y       |
| ECGs                            | Y [5] [2]               |        | Y       |
| Physical Examination            | Y[6] [2]                |        | Y       |
| Focused ENT Examination         | Y[7] [2]                |        | Y       |

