- [T14.1.9.8.3 Shift Tables for Changes from Baseline in ECG Interpretation to End of Treatment \(Safety Analysis Set\)](#)
- [T14.1.9.9 Summary of Physical Examinations \(Safety Analysis Set\)](#)
- [T14.1.9.10.1 Summary of Focused ENT Examination \(Safety Analysis Set\)](#)
- [T14.1.9.10.2 Summary of Potentially Clinical Significant Focused ENT Examination \(Safety Analysis Set\)](#)
- [T14.1.9.11.1 Summary of Extent of Exposure during the Post Randomization Treatment Period \(Safety Analysis Set\)](#)
- [T14.1.9.11.2 Summary of Rescue Medication \(Safety Analysis Set\)](#)
- [T14.1.9.12.1 Summary of Average AM rTNSS \(Full Analysis Set\)](#)
- [T14.1.9.12.2 Summary of Repeated Measures Analysis Results in Average AM rTNSS over the First 6, 30, and 52 Weeks of Treatment \(Full Analysis Set\)](#)
- [T14.1.9.12.3 Summary of Average AM rTNSS \(Per Protocol Set\)](#)
- [T14.1.9.12.4 Summary of Repeated Measures Analysis Results in Average AM rTNSS over the First 6, 30, and 52 Weeks of Treatment \(Per Protocol Set\)](#)

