- [L16.2.6.11 Listing of Change from Baseline in Physician Assessed Nasal Symptom Scores \(PNSS\) \(Safety Analysis Set\)](#)
- [L16.2.6.12 Listing of Rhinitis Control Assessment Test \(RCAT\) \(Safety Analysis Set\)](#)
- [L16.2.6.13 Listing of Change from Baseline in Rhinitis Control Assessment Test \(RCAT\) \(Safety Analysis Set\)](#)
- [L16.2.7.1 Listing of Treatment Emergent Adverse Events by Treatment During Randomized Treatment Period \(Safety Analysis Set\)](#)
- [L16.2.7.2 Listing of Adverse Events During Placebo Run-in Period](#)
- [L16.2.7.3 Listing of Pre-Treatment Adverse Events \(Safety Analysis Set\)](#)
- [L16.2.8.1 Listing of Clinical Laboratory Test Results \(Biochemistry\) \(Safety Analysis Set\)](#)
- [L16.2.8.2 Listing of Clinical Laboratory Test Results \(Hematology\) \(Safety Analysis Set\)](#)
- [L16.2.8.3 Listing of Clinical Laboratory Test Results \(Urinalysis\) \(Safety Analysis Set\)](#)
- [L16.2.8.4 Listing of Pregnancy Test Results \(Safety Analysis Set\)](#)
- [L16.2.8.5 Listing of Vital Signs \(Safety Analysis Set\)](#)
- [L16.2.8.6 Listing of 12-Lead ECGs \(Safety Analysis Set\)](#)
- [L16.2.8.7 Listing of Physical Examination \(Safety Analysis Set\)](#)
- [L16.2.8.8 Listing of Focused ENT Examination \(Safety Analysis Set\)](#)
- [L16.2.8.9 Listing of Eye Examination \(Safety Analysis Set\)](#)

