| GSP 301 placebo NS pH [REDACTED] |                                |         |                    |                                  |                                |
| GSP 301 NS                       |                                |         |                    |                                  |                                |

CS= Clinically Significant; NCS= Not Clinically Significant;

Data source: xx

Created on: ddmmmyy hh:mm

Page 1 of N

|  |                                    |                                  |
|--|------------------------------------|----------------------------------|
| Protocol Number:
GPL/CT/2014/018/III
(Study No. GSP 301-303) | SAP Version Number:
Version 1.0 | SAP Version Date:
04-Apr-2017 |
|--|------------------------------------|----------------------------------|

**L16.2.8.9 Listing of Eye Examination  
(Safety Analysis Set)**

[figure not shown]
| Treatment Group                  | Subject / Randomization Number | Visit    | Eye Examination Date | Results Right Eye | Results Left Eye |
|----------------------------------|--------------------------------|----------|----------------------|-------------------|------------------|
| GSP 301 placebo NS pH [REDACTED] | xx-xxx/xxxxx                   | Visit 1  | ddmmmyyy             | Normal            | Normal           |
|                                  |                                | Visit 2  |                      |                   |                  |
|                                  |                                | Visit 3  |                      |                   |                  |
|                                  |                                | Visit 4  |                      |                   |                  |
|                                  |                                | etc      |                      |                   |                  |
|                                  |                                | Visit 12 |                      |                   |                  |
| GSP 301 placebo NS pH [REDACTED] |                                |          |                      |                   |                  |
| GSP 301 NS                       |                                |          |                      |                   |                  |

Data source: xx  
Created on: ddmmmyy hh:mm

Page 1 of N

|  |                                    |                                  |

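### The SAP plans no by-group summary of the focused eye examination, although it is a named part of a primary safety endpoint and the protocol plans one

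*SAP*

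**What the plan says.** SAP 4.1 lists among the primary endpoints "Vital signs, physical examinations (PE), and focused ears, nose, and throat (ENT) and eye examinations at baseline, Week 30, and Week 52". The protocol synopsis has the same endpoint.

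Protocol 13.7.7 plans the analysis: "Descriptive statistics will be used to summarize ENT and eye examination results by treatment group and time point (Week 30 and Week 52"). It continues: "The number of subjects with findings of potential clinical significance will be tabulated. All ENT and eye examination data will be displayed in listings".

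SAP 12.2.9 is headed for the ENT examination alone. It says that descriptive statistics "will be used to summarize ENT examination results by treatment group and time point (Screening Visit, Week 30 and Week 52"), adds a tabulation of potentially clinically significant values and a listing, and never mentions the eye. In SAP Table 2 the corresponding row is "Focused ENT Examination", with no row for the eye. The list of tables has T14.1.9.10.1, a summary of the focused ENT examination, and "T14.1.9.10.2 Summary of Potentially Clinical Significant Focused ENT Examination". The only planned display of the focused eye examination is "L16.2.8.9 Listing of Eye Examination".

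**The concern.** Long-term safety is this trial's primary objective. Protocol 12.4.11 has the eyes examined partly to look for known complications of intranasal corticosteroids and antihistamines. A reader of the study report would expect to see, for each group, how many subjects had the focused eye examination at each endpoint time point and how many were abnormal.

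If the SAP is followed exactly, that comparison is not produced. Abnormal findings judged not clinically significant would be visible only by counting through a listing, and so would the number actually examined. The latter matters because the sample-size section assumes 50% attrition by Week 52. The change is also undeclared, so nobody can tell whether it was a decision or a drafting slip.

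**Working it through.** No estimate or test is involved, so the check sets the passages side by side and counts displays.

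**Planned against provided**

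| Item | Protocol 13.7.7 | SAP: ENT | SAP: eye |
|---|---|---|---|
| Descriptive summary by group and time point | ENT and eye | T14.1.9.10.1 | none |
| Tabulation of potentially clinically significant findings | ENT and eye, read from the section heading | T14.1.9.10.2 | none |
| Listing | ENT and eye | L16.2.8.8 | L16.2.8.9 |

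Tables: ENT 2, eye 0.

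**Could ENT be shorthand for ENT and eye?** The shells rule this out.

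- T14.1.9.10.1 names nasal irritation, epistaxis, mucosal edema, nasal discharge, mucosal erythema, mucosal crusting, throat irritation, candidiasis and postnasal drip. That is 6 nasal + 3 throat = 9 items, with no eye item.
- L16.2.8.8 holds the same nine evaluations.
- T14.1.9.10.2 is to be continued for further evaluations, but under a focused ENT title, and the matching listing has no eye evaluation.
- The eye examination has its own listing with a different layout. The SAP's schedule in Appendix 2 names both examinations when it means both.

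**Is the change declared?** SAP 1.0 lists four changes: MMRM in place of ANCOVA, optional multiple imputation, the randomization description, and the FAS definition. Changes concerning the eye examination: 0 of 4. Protocol section 13 says the SAP prevails where the two differ.

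**Size of the gap**

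- Against the endpoint time points (baseline, Week 30, Week 52): 3 groups × 3 times = 9 cells without a count.
- Against the two time points named in protocol 13.7.7: 3 × 2 = 6 cells.

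**What other outputs cover**

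- Protocol 12.4 has clinically significant abnormal safety findings recorded as adverse events, unless they belong to the underlying disease and are no worse than expected. Those recorded reach the by-group adverse-event tables.
- SAP 12.2.3 puts glaucoma, raised intraocular pressure and cataract in the special-interest tables.
- The physical examination has one item rating head and eyes together. The T14.1.9.9 shell tabulates it by group at Visits 1, 8 and 12.

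None of these gives the number examined, or the number abnormal, on the focused eye examination.

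**Source for a significance tabulation.** The L16.2.8.9 shell has "Results Right Eye" and the matching left-eye column, but no separate clinical-significance column. L16.2.8.8 does have one.

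**The case against.** The strongest reply is that this is a drafting omission with little safety content at stake. Significant eye findings are mostly captured as adverse events and compared by group, the main ocular risks have special-interest tables, and the physical examination gives a by-group view of head and eyes at the three endpoint time points. The SAP has no hypotheses, the eye data are collected and listed by treatment, and Appendix 1 allows further tables. Most of this stands and limits the point. But adverse-event tables count events after investigator judgement, the physical-examination item merges two regions, and the clause on further tables is post hoc and prespecifies nothing.

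Other objections have some force:

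- Only the first sentence of protocol 13.7.7 names the eye and the grouping. Reading the significance tabulation as by-group and covering the eye is natural, but it is an inference from the heading.
- The count of 9 takes baseline from the endpoint. Protocol 13.7.7 alone gives 6.
- The missing significance column is weak evidence. Other SAP shells carry significance inside the result column, and shells show only the general layout. Whether the CRF collects it for the eye cannot be seen here.
- SAP silence might be read as leaving protocol 13.7.7 in force. That is arguable, but SAP 12.2.9, Table 2 and the list of tables all specify ENT alone, so a programmer working from them would produce no eye table.

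**Conclusion.** The concern holds. A named component of a primary safety endpoint has no by-group summary in the SAP: 0 tables for the eye against 2 for ENT, and 9 group-by-time cells without a count (6 on the protocol's own time points). The departure from protocol 13.7.7 is not declared.

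The consequence is moderate. Nothing inferential changes, and clinically significant findings mostly surface elsewhere. What is lost is the number examined and the number abnormal per group, including abnormalities judged not clinically significant. The conclusion rests on the shells meaning what their titles and items say, and on the SAP governing where it differs from the protocol. It should be corrected before database lock.

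**What to change.** - Add the focused eye examination to SAP 12.2.9, to Table 2 and to the list of tables.
- Show results by treatment group at baseline, Week 30 and Week 52, with the number examined as denominator, and tabulate findings of potential clinical significance.
- State the baseline. The protocol 13.7 default is the last assessment before the first randomized dose, normally Visit 2 for this examination, whereas SAP 12.2.9 summarizes ENT from the Screening Visit. Apply one rule to both, or say why they differ. Showing all visits, as the ENT shells already do, would display Visits 1 and 2 together.
- State how the two eyes are combined per subject, for example abnormal if either eye is abnormal.
- Check the CRF for a clinical-significance field for the eye. If it exists, show it in L16.2.8.9.
- If the omission is intended, declare and justify it in SAP 1.0.

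The cost is one or two descriptive tables and a few lines of SAP text. Study conduct does not change, and right-eye and left-eye results are already in the listing shell.

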### **12.2.10 Rescue Medication**

|   |                                    |                                  |
|---|------------------------------------|----------------------------------|
|  | STATISTICAL ANALYSIS PLAN   |                                  |
| Protocol Number:
GPL/CT/2014/018/III
(Study No. GSP 301-303)                | SAP Version Number:
Version 1.0 | SAP Version Date:
04-Apr-2017 |

Descriptive statistics will be used to summarize the number and percentage of subjects who used rescue medication by treatment and rescue medication categories.

Rescue medication along with the type, dose, and duration of rescue medication will be listed by treatment and subject.

### 12.3 Efficacy Analyses of Efficacy Endpoints

For all efficacy statistical analysis of efficacy endpoints, the comparison of interest will be GSP 301 NS vs. placebo NS pH [REDACTED]. The statistical analysis will only include up to week 52 data in the analysis.

#### 12.3.1 Overview of Efficacy Analysis of the Efficacy Endpoints (rTNSS, iTNSS, RQLQ(S) over the first 6, 30, and 52 weeks of treatment)

The efficacy analysis of the efficacy endpoints will be performed on the FAS (primary) and the PPS (supportive) for rTNSS and iTNSS. For RQLQ(S) outputs will be performed on the FAS.

[Table 3](#) provides an overview of the planned efficacy analyses.

|  |                                    |                                  |
|--|------------------------------------|----------------------------------|
| Protocol Number:
GPL/CT/2014/018/III
(Study No. GSP 301-303) | SAP Version Number:
Version 1.0 | SAP Version Date:
04-Apr-2017 |
|--|------------------------------------|----------------------------------|

**Table 3: Overview of Planned Efficacy Analyses**

|  | Stats Analysis |   | Summary |   | Individual |
|--|----------------|---|---------|---|------------|
|  | T              | F | T       | F | L          |
| Change from baseline in the average AM rTNSS over the first 6, 30, and 52 weeks of treatment |                |   |         |   |            |
| rTNSS – MMRM – FAS   | Y              | Y |         |   |            |
| rTNSS – MMRM – PPS   | Y              | Y |         |   |            |
| rTNSS Raw Data   |                |   |         |   |            |
| By Day (including post-baseline and change from baseline) - SAS                              |                |   |         |   | Y          |
| Change from baseline in the average AM iTNSS over the first 6, 30, and 52 weeks of treatment |                |   |         |   |            |
| iTNSS – MMRM – FAS   | Y              | Y |         |   |            |
| iTNSS – MMRM – PPS   | Y              | Y |         |   |            |
| iTNSS Raw Data   |                |   |         |   |            |
| By Day (including post-baseline and change from baseline) - SAS                              |                |   |         |   | Y          |
| Change from baseline in the overall RQLQ(S) score at Weeks 6, 30, and 52                     |                |   |         |   |            |
| RQLQ(S) – MMRM – FAS   | Y              | Y | Y       |   |            |
| RQLQ(S) Raw Data   |                |   |         |   |            |
| Visit (including post-baseline and change from baseline) - SAS                               |                |   |         |   | Y          |

